11.3 Adverse events of special interest

An AE of special interest is any AE that a regulatory authority has mandated be reported on an expedited basis, regardless of the seriousness, expectedness, or relatedness of the AE to the administration of a UCB product/compound.

The following are AEs of special interest:

- The following arrhythmias: atrial fibrillation/flutter, ventricular tachycardia or fibrillation, AV block (2nd degree Type I and II and 3rd degree), and marked bradycardia (<45bpm)
- Syncope or loss of consciousness (other than seizure related)
- Serious suspected multiorgan hypersensitivity reactions

Serious suspected multiorgan hypersensitivity cases may be identified and reported to the sponsor by the investigator using the following algorithm as agreed with the United States Food and Drug Administration:

An AE or laboratory value (as defined in the following text) suggestive of internal organ involvement (including but not limited to hepatitis, nephritis, pneumonitis, carditis, colitis, encephalitis, pancreatitis, myositis, arthritis, or hematologic system involvement) combined with at least 1 of the following: fever, rash, lymphadenopathy, or eosinophilia.

Treatment-emergent abnormal laboratory value criteria suggestive of internal organ involvement or eosinophilia:

- Eosinophils % $\geq 10\%$
- Eosinophils absolute $\geq 0.5\text{G/L}$
- Neutrophils absolute $< 1.5\text{G/L}$
- Platelets $\leq 100\text{G/L}$
- ALT $\geq 2 \times \text{ULN}$
- AST $\geq 2 \times \text{ULN}$

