The incidence of drug-related TEAEs by seriousness will be presented for each treatment group by MedDRA primary SOC and PT.

The incidence of TEAEs by dose at onset will be presented for each treatment group by MedDRA primary SOC and PT, and will be repeated by treatment group and age group, and by treatment group and weight group using the levels defined in section 4.8.

The incidence of non-serious TEAEs occurring in at least 5% of subjects in any treatment group will be summarized for each treatment group by MedDRA primary SOC and PT, and will be repeated by treatment group and age group, using the levels defined in section 4.8.

Other significant AEs, defined in Appendix 12 (section 12.2), will be summarized for each treatment group by MedDRA primary SOC and PT, and will be repeated by treatment group and weight group, using the levels defined in section 4.8.

In addition, summaries for the incidence of TEAEs overall, incidence of serious TEAEs, incidence of TEAEs leading to discontinuation of study medication, and incidence of other significant TEAEs will be repeated presenting the site and subject number of all those subjects experiencing each TEAE. Subject data listings will also be presented.

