## 12 APPENDICES

### 12.1 Marked abnormality criteria for laboratory data

#### 12.1.1 Marked abnormality criteria for hematology data

**Table 12–1: Hematology abnormality criteria**

Parameter	Age Range	Unit (conventional)	Abnormality criteria (conventional unit)	Unit (standard)	Abnormality criteria (standard unit)
Hematocrit	<2y	%	≤27 >45	%	≤27 >45
	2y - <17y	%	≤29 >47	%	≤29 >47
	≥17y	%	≤85% of LLN ≥115% of ULN	%	≤85% of LLN ≥115% of ULN
Hemoglobin	<2y	g/dL	≤9.0 >15.0	g/L	≤90 >150
	2y - <17y	g/dL	≤9.5 >16.0	g/L	≤95 >160
	≥17y	g/dL	≤85% of LLN ≥115% of ULN	g/L	≤85% of LLN ≥115% of ULN
WBC/ Leukocytes	All	10  /L	≤3.0 ≥16.0	G/L	≤3.0 ≥16.0
Lymphocytes Absolute	<2y	10  /L	<1.0 >9.8	G/L	<1.0 >9.8
	2y - <6y	10  /L	<0.7 >6.9	G/L	<0.7 >6.9
	≥6y	10  /L	<0.6 >5.0	G/L	<0.6 >5.0
Basophils	>1m	%	≥5.0	%	≥5.0
Basophils Absolute	>1m	10  /L	≥0.4	G/L	≥0.4
Eosinophils	>1m	%	≥10	%	≥10
Eosinophils Absolute	>1m	10  /L	≥1.0	G/L	≥1.0
Monocytes	>1m	%	≥20.0	%	≥20.0

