**Table 12–1: Hematology abnormality criteria**

Parameter	Age Range	Unit (conventional)	Abnormality criteria (conventional unit)	Unit (standard)	Abnormality criteria (standard unit)
Monocytes Absolute	>1m	10  /L	≥2.0	G/L	≥2.0
Neutrophils Absolute	>1m	10  /L	<1.5	G/L	<1.5
Platelets	>1m	10  /L	≤100 ≥600	G/L	≤100 ≥600
RBC/ Erythrocytes	<2y	10  /L	<3.0	T/L	<3.0
	≥2y	10  /L	<3.5	T/L	<3.5

Abbreviations: m =month, y = year. A month is defined as 30 days; a year is defined as 365.25 days.

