**12.1.2 Marked abnormality criteria for chemistry data**

**Table 12–2: Chemistry abnormality criteria**

Parameter	Age Range	Unit (conventional)	Abnormality criteria (conventional unit)	Unit (standard)	Abnormality criteria (standard unit)
AST (SGOT)	All	U/L	≥3.0 x ULN ≥5.0 x ULN ≥10.0 x ULN	U/L	≥3.0 x ULN ≥5.0 x ULN ≥10.0 x ULN
ALT (SGPT)	All	U/L	≥3.0 x ULN ≥5.0 x ULN ≥10.0 x ULN	U/L	≥3.0 x ULN ≥5.0 x ULN ≥10.0 x ULN
Alkaline Phosphatase	<4y	U/L	≥690	U/L	≥690
	4y - <10y	U/L	≥834	U/L	≥834
	10y - <17y	U/L	≥1761	U/L	≥1761
	≥17y	U/L	≥3.0 x ULN	U/L	≥3.0 x ULN
GGT	<6m	U/L	≥522	U/L	≥522
	6m - <1y	U/L	≥279	U/L	≥279
	1y - <13y	U/L	≥66	U/L	≥66
	13y - <17y	U/L	≥126	U/L	≥126
	≥17y	U/L	≥3.0 x ULN	U/L	≥3.0 x ULN

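### The SAP's list of other significant AEs covers two of the protocol's three special-interest groups; nothing planned identifies or counts suspected multiorgan hypersensitivity by arm

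*SAP*

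**What the plan says.** Protocol 11.3 defines an adverse event of special interest as one that a regulatory authority requires to be reported on an expedited basis. The third of its three groups is "Serious suspected multiorgan hypersensitivity reactions". For it the section gives an algorithm agreed with the FDA: an adverse event or laboratory value pointing to internal organ involvement, "combined with at least 1 of the following: fever, rash, lymphadenopathy, or eosinophilia". Six laboratory limits accompany the algorithm.

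SAP 10.2 plans tables of TEAEs, serious TEAEs and TEAEs leading to discontinuation by SOC and PT, repeated with site and subject numbers. It adds: "Other significant AEs, defined in Appendix 12 (section 12.2), will be summarized for each treatment group by MedDRA primary SOC and PT". SAP 12.2 lists hepatotoxicity (two terms), cardiac and ECG terms, suicidality terms, and loss of consciousness and syncope. It has no term for hypersensitivity, rash, fever, lymphadenopathy or eosinophilia.

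SAP 12.1 gives marked-abnormality limits, one laboratory parameter at a time. SAP 10.3 counts values beyond these limits only within the Treatment Period (Titration plus Maintenance).

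**The concern.** Multiorgan hypersensitivity is defined by findings that occur together. Unless the investigator records it as one diagnosis, it reaches the database in pieces: a rash, a fever, a raised transaminase, a raised eosinophil count. Tables by PT and by laboratory parameter count each piece separately and cannot show how many children had the combination.

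The SAP deals with the other two special-interest groups. Section 12.2 has terms for the arrhythmias and for syncope or loss of consciousness. SAP 10.4.1 goes further for marked bradycardia: it combines a pulse rate below 45 bpm with an adverse event coded to bradycardia and plans a listing. Joining a measurement to an adverse event is therefore already within the SAP's practice. It is absent for the one special-interest event whose definition depends on such a join. At stake is whether the report can state, by arm, how many children had this event.

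**Working it through.** No sample size, power or alpha figure bears on this, so there is no plan figure to reproduce. The check sets the documents side by side.

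**1. Special-interest groups (Protocol 11.3) against SAP 12.2**

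| Protocol 11.3 group | Terms in SAP 12.2 |
|---|---|
| Listed arrhythmias, including marked bradycardia | Yes; also a pulse-plus-AE rule in SAP 10.4.1 |
| Syncope or loss of consciousness | Yes |
| Serious suspected multiorgan hypersensitivity | None |

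Two of three groups are covered.

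**2. Laboratory limits (Protocol 11.3) against SAP Tables 12-1 and 12-2**

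| Parameter | Protocol 11.3 | SAP 12.1 | Same? |
|---|---|---|---|
| Eosinophils, % | ≥10 | ≥10 | Yes |
| Eosinophils, absolute (G/L) | ≥0.5 | ≥1.0 | No |
| Neutrophils, absolute (G/L) | <1.5 | <1.5 | Yes |
| Platelets, low (G/L) | ≤100 | ≤100 | Yes |
| ALT (x ULN) | ≥2 | from ≥3 | No |
| AST (x ULN) | ≥2 | from ≥3 | No |

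The SAP tiers for ALT and AST are "≥3.0 x ULN ≥5.0 x ULN ≥10.0 x ULN". Three of the six limits agree and three differ.

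**3. One child through both sets of rules (assumed values)**

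ALT 2.5 x ULN, AST 2.2 x ULN, WBC 8.75 G/L, eosinophils 0.7 G/L, neutrophils 4.0 G/L, platelets 250 G/L. Eosinophil percentage = 100 x 0.7 / 8.75 = 8.0%.

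- Protocol 11.3: ALT and AST meet the organ part (2.5 ≥ 2; 2.2 ≥ 2). Absolute eosinophils meet the systemic part (0.7 ≥ 0.5). The algorithm is satisfied.
- SAP 12.1: 2.5 < 3, 2.2 < 3, 0.7 < 1.0, 8.0 < 10, 4.0 ≥ 1.5, 250 > 100. It flags 0 of the 6 parameters.
- SAP 12.2: no term applies to these findings.

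The result is the same for any ALT and AST of 2 to <3 x ULN with absolute eosinophils of 0.5 to <1.0 G/L and below 10%.

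**4. Why equal limits would not close the gap**

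Suppose an arm of n children has a with an organ finding and b with a systemic sign. Separate tables report a and b. The number with both can lie anywhere from max(0, a + b − n) to min(a, b), which for uncommon findings means from none to all of the smaller group. The count of interest is not recoverable from the separate counts, whatever limits are used.

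**5. Time windows**

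- TEAEs (SAP 10.2): first dose to 30 days after last dose.
- Laboratory marked abnormalities (SAP 10.3): first dose to the end of the Treatment Period.
- Placebo subjects entering the Transition Period first receive LCM there (Protocol 7.2.3). Their chemistry and hematology at Week 20 (Protocol Table 5-2) fall outside the marked-abnormality table.

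**The case against.** The case on the other side is substantial, and much of it stands.

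- **The child is not lost.** Every reported component is counted under its own PT, and a serious one also in the serious TEAE table, both repeated with subject numbers. Laboratory data are fully listed. Protocol 11.1.3 asks investigators to record the overall diagnosis, so a recognised case may appear under one term. This stands. What remains missing is any output that makes the link; a reader would have to match subject numbers across tables and listings by hand.
- **The IDMC.** A reader might infer that serious cases would escape the IDMC because SAP 4.3 points to the 12.2 list. The documents do not support that. SAP 4.3 triages SAEs as well as the 12.2 events, and Protocol 11.4 requires special-interest events to be reported immediately. The detailed procedures are in a charter that is not part of these documents.
- **The laboratory limits.** A reader might take the three differing limits in SAP 12.1 as errors. They are not. Those limits define marked abnormality for single parameters; the 11.3 limits are lower screening values meant for use in combination. The SAP's 3x and 5x ULN tiers match thresholds in the protocol's own liver criteria (6.3 and 11.7).
- **No broken commitment.** Protocol 13.4.1 promises no special-interest table, and 11.3 offers the algorithm as an aid to investigator reporting. This stands: the point is a gap between Protocol 11.3 and the SAP's outputs, not a departure from a stated analysis.
- **The algorithm is not ready to program.** Its organ list is open-ended, fever has no threshold, no time window links the components, and one laboratory list serves both organ involvement and eosinophilia. This stands and belongs in the cost of the fix.

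**Conclusion.** The point holds in a limited form. SAP 12.2 covers two of the three special-interest groups in Protocol 11.3, and no planned table or listing identifies multiorgan hypersensitivity cases or counts them by arm. The SAP gives no reason for leaving the group out. Its single-parameter laboratory summaries cannot fill the gap, because they do not join findings within a child and because they end before the TEAE window does.

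The consequence is one missing safety count, not missing data. The number of children affected cannot be estimated from the documents. The worked case uses assumed values and shows only that a child can satisfy the laboratory route of the algorithm without triggering a limit in 12.1 or a term in 12.2. Whether such a case is serious, as the protocol item requires, is a separate judgement.

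This is worth changing because it is cheap. It does not bear on the primary or secondary efficacy analyses.

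**What to change.** Leave SAP 12.1 as it is. Add to SAP 10.2 and 12.2 a category of suspected multiorgan hypersensitivity, made up of:

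1. cases reported as such by investigators; and
2. subjects flagged by the Protocol 11.3 algorithm, using the 11.3 laboratory limits over the TEAE window.

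Before unblinding, write down:

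- the PT list for organ involvement and for each systemic sign, including how fever is identified;
- the time window within which the two components must fall;
- which laboratory values can serve as the organ component and which as eosinophilia, so that one value does not fill both roles;
- how values already beyond a limit at Baseline are handled, since 11.3 refers to treatment-emergent values.

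Have flagged subjects medically reviewed under blind. Tabulate serious cases by arm, with all flagged cases as supportive, and list the subjects. Show the Transition Period separately, because subjects randomized to placebo receive LCM in it. If the sponsor prefers not to do this, the SAP should say why.

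Cost: SAP text, one derivation, a few table rows and one listing. It uses adverse event and laboratory data already collected. Agreeing the definitions is the larger part of the work. The downside is that the low limits will flag some non-specific cases, each needing medical review.

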### 10.3 Clinical laboratory evaluations

Hematology, blood chemistry (including liver function tests), urinalysis, and endocrinology parameters are assessed throughout the study from Visit 1 (entry to study) to Visit 8, and at ETV in case of early termination, and may also be assessed at unscheduled visits. Laboratory parameters will also be assessed during the Transition Period (except endocrinology), Taper Period, and at the Safety Follow-Up Visit.

Urinalysis will be performed for subjects  $\geq 5$  years of age only. All summaries of laboratory parameters will only summarize parameters planned based on the protocol. However, both planned and unplanned laboratory parameters will be provided in subject data listings. Summaries will include hematology, chemistry and endocrinology results; urinalysis results will be included in subject data listings only.

Observed values of hematology, chemistry, and non-gender specific endocrinology parameters (ie, thyroid stimulating hormone, triiodothyronine [total and serum-free], and thyroxine [total and serum-free]), and change from Baseline will be summarized by treatment group for all post-Baseline visits, and Last Visit. Gender specific endocrinology parameters (ie, follicle stimulating hormone, luteinizing hormone, and testosterone) will be presented similarly, by treatment group and gender.

Treatment-emergent markedly abnormal (TEMA) values are defined as those TEMA values which occur during the defined Treatment Period (see Section 3.2.2) at scheduled or unscheduled visits on or after the first study medication administration through to the end of the Treatment Period.

The number and percentage of subjects with a TEMA value, TEMA low value, and TEMA high value will be summarized for each treatment group at each post-Baseline visit and Last Visit. Percentages will be relative to the number of subjects with a value at each visit. Criteria for determining if a value is TEMA are detailed in Appendix 12.1.

A serum pregnancy test will be performed on all females of childbearing potential at Visit 1 (entry to study), Visit 4, Visit 5, Visit 7, Visit 8, and at ETV in case of early termination. A serum pregnancy test will also be performed during the Taper Period, and at the Safety Follow-Up Visit, but only at the Safety Follow-Up Visit if blood is collected for other laboratory tests, otherwise a urine pregnancy test will be performed.

A urine pregnancy test will be performed at Visit 2 (Baseline), Visit 3, and Visit 6. A urine pregnancy test will also be performed at Visit 4 of the Transition Period, and at the Safety Follow-Up Visit, but only at the Safety Follow-Up Visit if a serum pregnancy test has not been performed.

A listing of serum pregnancy test results and urine pregnancy test results will be provided. No summaries of these results are planned.

## **10.4 Vital signs, physical findings, and other observations related to safety**

### **10.4.1 Vital signs, body weight, height, BMI, and head circumference**

Vital signs (systolic BP [SBP], diastolic BP [DBP], and pulse rate) will be assessed after at least 3 minutes at rest in a supine position throughout the study from Visit 1 (entry to study) to Visit 8, and at ETV in case of early termination, and at unscheduled visits. Vital signs will also be assessed during the Transition Period, Taper Period, and at the Safety Follow-Up Visit.

Assessment of orthostatic changes will also be performed as follows: After the 3 minute measurement in supine position, the subject is asked to stand up, and SBP, DBP and pulse rate are taken approximately 1 minute and approximately 3 minutes after the subject stands up as feasible.

Body weight will be assessed throughout the study from Visit 1 (entry to study) to Visit 8, and at ETV in case of early termination, and at unscheduled visits. Body weight will also be assessed during the Transition Period, Taper Period, and at the Safety Follow-Up Visit.

Height will be assessed at Visit 1 (entry to study), Visit 2 (Baseline), Visit 8, and at ETV in case of early termination. BMI will subsequently be calculated at these visits.

Head circumference will be assessed at Visit 1 (entry to study), Visit 8, and at ETV in case of early termination.

Observed values of SBP, DBP, pulse rate, body weight, height, BMI, and head circumference will be summarized by treatment group for each visit and Last Visit. Change from Baseline for SBP, DBP, pulse rate, body weight, height, BMI and head circumference will be summarized by treatment group for all post-Baseline visits, and Last Visit, as appropriate.

Orthostatic changes of SBP, DBP, and pulse rate will be summarized by treatment group for each visit and Last Visit.

Markedly abnormal (MA) values are defined as those MA values which occur during the defined Treatment Period (see Section 3.2.2) at scheduled or unscheduled visits on or after the first study medication administration through to the end of the Treatment Period.

The number and percentage of subjects with a MA value, MA low value, and MA high value, at each post-Baseline visit up to Visit 8, for which SBP, DBP, pulse rate, and body weight were

scheduled to be assessed, and Last Visit, will be presented. Percentages will be relative to the number of subjects with a value at each visit.

The abnormal vital sign criteria are defined as follows:

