^c If an Unscheduled Visit is needed (eg, due to AE), then the assessments noted will be performed. Additional assessments may be performed at the investigator's discretion. The C-SSRS will be completed at an Unscheduled Visit only if the visit is related to an AE.

^d Medical history to include demographics (date of birth [where permitted], age group category, age in months and years, race, ethnicity, and gender).

^e Only applicable for subjects with an implanted VNS device.

^f The Tanner Stage will be performed only for subjects who are pubescent at Visit 1 or who enter puberty during the course of the study.

^g The subject's body weight at Baseline (Visit 2) will be used to determine dose throughout the study.

^h A 12-lead ECG (2 interpretable recordings) will be performed prior to any blood draws and vital signs assessment. The subject should rest in the supine position for approximately 5 minutes before the recordings and during the recordings, if possible. The recordings should be made 20 to 30 minutes apart.

ⁱ Urinalysis will be performed for subjects ≥ 5 years of age only.

- ^j Pregnancy tests will be performed for female subjects of childbearing potential only.
- ^k Blood samples for analysis of concomitant AED plasma concentrations and/or LCM will be drawn along with clinical chemistry, hematology, and endocrinology samples, as applicable.
- ^l The C-SSRS will be completed for all subjects ≥ 6 years of age. The C-SSRS will be completed at an Unscheduled Visit only if the visit related to an AE.
- ^m The Achenbach CBCL: CBCL/1½ -5 for children 18 months to 5 years and 11 months of age, and CBCL/6-18 for children ≥ 6 years to < 17 years of age at Screening; to be completed by the parent(s)/legal representative(s) (estimated completion time 45 minutes). For each subject, the same version of the scale that was completed at Visit 2 (CBCL/1½ -5 or CBCL/6-18) should be maintained for the duration of the study and should be completed by the same parent/legal representative. The Achenbach CBCL will be used only in countries where a translated version is available.

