At each clinic visit and telephone contact, the investigator, in conjunction with the subject and/or parent(s)/legal representative(s), will decide how to proceed with study medication dosing based on tolerability (including vital signs, body weight, 12-lead ECG, and AE reporting, as applicable to the type of contact). If the withdrawal of study medication is required during the Titration Period, the subject will enter the blinded Taper Period (Section 8.5).

8.2.1 Titration Period: Telephone Contact 2 (Week 1), Telephone Contact 3 (Week 3), and Telephone Contact 4 (Week 5)

During the Titration Period telephone contacts (Telephone Contact 2, Telephone Contact 3, and Telephone Contact 4), the following assessments will be performed:

- Concomitant medications
- Concomitant AEDs
- Reminder to complete subject diary on a daily basis
- Review withdrawal criteria
- AE reporting

8.2.2 Titration Period: Visit 3 (Week 2), Visit 4 (Week 4), and Visit 5 (Week 6)

During the Titration Period clinic visits (Visit 3, Visit 4, and Visit 5), the following assessments will be performed:

- Concomitant medications
- Concomitant AEDs
- VNS assessment (for subjects with an implanted VNS device)
- Physical examination (brief)
- Vital signs (BP and pulse rate, including orthostatic assessments)
- Body weight assessment
- Neurological examination (brief)
- 12-lead ECG (2 interpretable recordings [20 to 30 minutes apart] to be performed prior to any blood draws and vital signs assessment and, if possible, with the subject in the supine position for approximately 5 minutes preceding the recordings and during the recordings)
- Blood sample for clinical chemistry and hematology (Visit 4 and Visit 5 only)
- Urine sample for urinalysis (for subjects ≥ 5 years of age) (Visit 4 and Visit 5 only)
- Serum pregnancy test (for females of childbearing potential) (Visit 4 and Visit 5 only)
- Urine pregnancy test (for females of childbearing potential) (Visit 3 only)
- Blood sample for determination of concomitant AED plasma concentration (Visit 5 only)

- Blood sample for determination of LCM plasma concentration (Visit 5 only)
- C-SSRS (for subjects ≥ 6 years of age)
- Achenbach CBCL (same version used at Visit 2) (Visit 5 only)
- Contact IXRS
- Dispense study medication
- Study medication return
- Reminder to complete subject diary on a daily basis
- Review withdrawal criteria
- AE reporting
- Health care resource use

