8.3.1 Maintenance Period: Visit 6 (Week 8) and Visit 7 (Week 12)

During Visit 6 and Visit 7 (clinic visits) of the Maintenance Period, the following assessments will be performed:

- Concomitant medications
- Concomitant AEDs
- VNS assessments (for subjects with an implanted VNS device)
- Physical examination (brief)
- Vital signs (BP and pulse rate; including orthostatic assessments)
- Body weight assessment
- Neurological examination (brief)

- 12-lead ECG (2 interpretable recordings [20 to 30 minutes apart] to be performed prior to any blood draws and vital signs assessment and, if possible, with the subject in the supine position for approximately 5 minutes preceding the recordings and during the recordings)
- Blood sample for clinical chemistry and hematology (Visit 7 only)
- Urine sample for urinalysis (for subjects ≥ 5 years of age) (Visit 7 only)
- Serum pregnancy test (for females of childbearing potential) (Visit 7 only)
- Urine pregnancy test (for females of childbearing potential) (Visit 6 only)
- C-SSRS (for subjects ≥ 6 years of age)
- Contact IXRS
- Dispense study medication
- Study medication return
- Reminder to complete subject diary on a daily basis
- Review withdrawal criteria
- AE reporting
- Health care resource use

The subject will be scheduled to return to the clinic as specified in [Table 5-1](#). The morning of the next clinic visit, the subject should take concomitant AEDs and study medication at the usual time(s).

8.3.2 Maintenance Period: Telephone Contact 5 (Week 10) and Telephone Contact 6 (Week 14)

During the Maintenance Period telephone contacts (Telephone Contact 5 and Telephone Contact 6); the following assessments will be performed:

- Concomitant medications
- Concomitant AEDs
- Reminder to complete subject diary on a daily basis
- Review withdrawal criteria
- AE reporting

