### **3.2.3 Mapping of assessments performed at Early Termination Visit**

Efficacy and safety assessments at an ETV that correspond to a scheduled visit will be summarized at the scheduled visit corresponding to the ETV if the assessment was scheduled to occur at that visit.

In particular, clinical laboratory parameters, vital signs, and body weight are assessed at all visits during the Treatment Period, and so all assessments of these variables at ETVs corresponding to a scheduled visit will be mapped to the corresponding scheduled visit.

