A listing of ECG data will be provided for all subjects with other significant TEAEs in the Cardiac and ECG Related Terms category defined in Appendix 12 (section 12.2). A subject data listing of all ECG parameter values for all subjects will also be presented. Listings will include results from each recording and the average of all recordings.

The number and percentage of subjects with treatment-emergent ECG abnormalities will be presented by visit and treatment group. Abnormalities reported at an unscheduled visit will be summarized under the scheduled visit preceding the unscheduled visit (if the abnormality was not present already at the preceding scheduled visit). Treatment-emergent is defined as meeting the criteria at any post-Baseline visit during the Treatment Period (including unscheduled visits)

and not meeting the same criteria during Baseline. All ECG parameter values will be listed for subjects meeting any abnormality criteria.

Abnormality criteria to be used in the determination of ECG abnormalities are defined as follows, where increase and decrease are relative to Baseline values:

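### A marked vital-sign abnormality found only at an unscheduled visit, and normal at the last assessment, enters no between-arm count; laboratory tests have a smaller inferred gap, and SAP 3.2.3 misstates the laboratory schedule

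*SAP*

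**What the plan says.** **Vital signs (SAP 10.4.1).** The definition is broad: "Markedly abnormal (MA) values are defined as those MA values which occur during the defined Treatment Period", at scheduled or unscheduled visits. The table is narrower. It gives the number and percentage with an abnormal value, "MA low value, and MA high value, at each post-Baseline visit up to Visit 8", restricted to visits at which the measure was scheduled, plus Last Visit.

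**Laboratory tests (SAP 10.3).** The definition again takes in unscheduled visits. The counts "will be summarized for each treatment group at each post-Baseline visit and Last Visit". The section does not say which row an unscheduled value belongs to.

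**ECGs (SAP 10.4.2).** Here there is a rule: "Abnormalities reported at an unscheduled visit will be summarized under the scheduled visit preceding the unscheduled visit", provided the abnormality was not already present at that scheduled visit.

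**Unscheduled visits.** Protocol Table 5-1, footnote c: "If an Unscheduled Visit is needed (eg, due to AE), then the assessments noted will be performed". Table 5-1 and Protocol 8.7 make vital signs, with orthostatic measures, a required assessment there. Laboratory tests are at the investigator's discretion.

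**Early Termination mapping (SAP 3.2.3).** The first sentence sends an Early Termination value to the corresponding scheduled visit only if that assessment was due at that visit. The next paragraph says "clinical laboratory parameters, vital signs, and body weight are assessed at all visits during the Treatment Period" and so maps all such values. For the Titration Period, Protocol 8.2.2 reads "Blood sample for clinical chemistry and hematology (Visit 4 and Visit 5 only". For Visits 6 and 7, Protocol 8.3.1 reads "Blood sample for clinical chemistry and hematology (Visit 7 only".

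**The concern.** For vital signs, the definition and the table do not match: a value can meet the definition and reach no row of the table built on it. Unscheduled visits are called, for example, because of an adverse event, so a pulse or blood pressure reading taken there is more informative than a routine one. A listing shows that the value exists but does not give a count by arm.

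SAP 3.2.3 raises a second problem. Two programmers could read its two paragraphs differently and produce different laboratory tables. Under one reading, the table gains rows for visits at which no laboratory test was due, filled mainly by children who were leaving the trial.

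**Working it through.** The plan states no figure on this point, so there is none to reproduce. The check counts scheduled assessments and then traces where an abnormal value would be counted.

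**1. Schedule (Protocol Table 5-1, 8.2.2, 8.3.1, 8.3.3).** There are six clinic visits after Baseline in the Treatment Period, Visits 3 to 8.

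| Assessment | Scheduled at | Share of visits |
|---|---|---|
| Vital signs, body weight | 3, 4, 5, 6, 7, 8 | 6 of 6 |
| Chemistry, hematology | 4, 5, 7, 8 | 4 of 6 |
| Endocrinology | 8 | 1 of 6 |

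All are also done at the Early Termination Visit (Protocol 8.8). The statement in SAP 3.2.3 is therefore right for vital signs and weight and wrong for laboratory tests.

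**2. Rows reached by an abnormal value.** Inputs are SAP 3.2.2 (the Treatment Period includes the Early Termination date), 3.2.3, 3.2.4 (Last Visit is the last non-missing Treatment Period value, scheduled or not), 10.3 and 10.4.1. For laboratory tests, I take the visit rows to be the scheduled visits.

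| Where the only abnormal value occurs | Row that counts it |
|---|---|
| Unscheduled visit, then normal at Visits 7 and 8 (vital signs or laboratory) | None |
| Unscheduled visit, then normal at Early Termination | None |
| Unscheduled visit that is the last assessment | Last Visit |
| Early Termination matching Visit 3 or 6, chemistry, first sentence of 3.2.3 | Last Visit |
| Same, second paragraph of 3.2.3 | Visit 3 or 6, and Last Visit |
| Early Termination matching no scheduled visit | Last Visit |

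Under the second paragraph, endocrinology could be placed in the same way at any of Visits 3 to 7.

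**3. Liver tests.** Protocol 6.3 and 11.7 call for repeat testing once transaminases reach 3 times the upper limit of normal (ULN). SAP Table 12-2 counts AST and ALT from the same 3 x ULN, and again at 5 and 10 x ULN. If the triggering value came at a scheduled visit, the child is already in that visit's 3 x ULN count. What can still be missed is a higher peak on a repeat test that has fallen back below 5 or 10 x ULN by the last assessment, or an elevation first found at an optional draw and later resolved.

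**4. Size.** The documents give no rate for abnormalities seen only at unscheduled visits. As an illustration, take an assumed proportion q of the planned 154 per arm. The expected number uncounted is 154 x q, and the chance of at least one is 1 - (1 - q)^154.

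| Assumed q | Expected per arm | Chance of at least one |
|---|---|---|
| 1% | 1.5 | 79% |
| 3% | 4.6 | 99% |
| 5% | 7.7 | over 99% |

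**5. Visit 3 and 6 rows under the second paragraph.** The planned 14% dropout gives 0.14 x 154 = 21.6 per arm. That is an upper figure, because the rate is for the overall study and can include dropouts in the Transition Period. Assume every Early Termination matches a clinic visit and they spread evenly: 21.6 / 6 = 3.6 per visit. One abnormal value among 3 or 4 children would print as 33% or 25%.

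**The case against.** Much of a broader criticism falls away.

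- A reader might infer that Early Termination values are lost. They are not. The Treatment Period runs through the Early Termination date, so these values enter Last Visit, as does any unscheduled value that is a child's last.
- A reader might infer that a child who comes in with syncope drops out of the comparison between arms. The documents do not support that. Syncope, loss of consciousness and bradycardia are among the other significant adverse events of SAP 12.2, which SAP 10.2 tabulates by arm, and adverse events are the primary safety variables. Only the accompanying measurement can be missing from a count. This does not close the gap, because the criteria in SAP Table 10-1 are numerical and do not depend on an adverse event being reported.
- The restriction to scheduled visits is explicit only for vital signs. For laboratory tests, it is inferred from the absence of a rule.
- The first sentence of SAP 3.2.3, applied with the protocol schedule, creates no Visit 3 or 6 laboratory rows. That is so, but the next paragraph says otherwise.
- It is tempting to add that 5% at each of six visits could mean anything from 5% to 30% ever abnormal. That bound holds for any by-visit table, rests on an invented rate, and does not measure what is lost at unscheduled visits.
- The ECG section has no any-time row either, so the form of the remedy is partly a choice. It does have an assignment rule, which vital signs and laboratory tests lack.

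All values also remain in listings, including a separate one for abnormal vital signs.

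**Conclusion.** The point stands in a limited form. For vital signs, the plan as written leaves out of every between-arm count an abnormality found at an unscheduled visit that is absent at scheduled visits and at the last assessment, although SAP 10.4.1 defines it as countable. For laboratory tests, the same gap is likely but inferred, and it is smaller because repeat liver tests usually follow a value already counted. SAP 3.2.3 is factually wrong on the laboratory schedule and contradicts itself. The consequence is misplaced or ambiguous visit rows, not lost data.

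The size is unknown. The counts and percentages in the working rest on assumed rates and an assumed even spread, and show scale only. Descriptive safety tables are affected; the primary efficacy analysis is not. The correction is still worth making, because it brings the tables into line with the SAP's own definitions.

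**What to change.** 1. In SAP 10.3 and 10.4.1, add a row for any time during the Treatment Period, covering scheduled, unscheduled and Early Termination values. Count each subject once per parameter and threshold. Use subjects with at least one post-Baseline value as the denominator. An assignment rule like the one for ECGs would also give these values a row, but the any-time row counts each subject once and matches the definition directly.
2. In SAP 3.2.3, state the protocol's schedule after Baseline in the Treatment Period: chemistry and hematology at Visits 4, 5, 7 and 8, endocrinology at Visit 8. Send an Early Termination laboratory value to a visit row only where that test was scheduled, and otherwise to the any-time and Last Visit rows.

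The cost is a short SAP wording change and one extra row per table. No new data are needed.
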